11.3.3.4.3 Supportive analyses

Supportive analysis will include an unadjusted model excluding the baseline stratification variable, an adjusted model including additional baseline covariates, model based on the PPS. Missing data imputation will be discussed in the SAP.

11.3.3.5 Longitudinal percent change from baseline over time in brain volume from baseline up to EOS

11.3.3.5.1 Hypothesis

The secondary endpoint percent change from baseline over time in brain volume up to EOS will be analyzed using a generalized linear mixed model to account for repeated measures, to compare the overall percent change in brain volume between the two treatment groups. The hypotheses are expressed as a linear combination of the fixed-effects and are tested at a two-sided significance level of 0.05:

$$H_0, \text{PCBV}: \mu_{\text{Ponesimod}} - \mu_{\text{Placebo}} = 0$$

vs

$$H_1, \text{PCBV}: \mu_{\text{Ponesimod}} - \mu_{\text{Placebo}} \neq 0$$

11.3.3.5.2 Analyses

The primary analysis of percent change from baseline in brain volume will be performed on the FAS using an adjusted generalized linear mixed model using the same approach as for the FSIQ-RMS secondary endpoint above [Section 11.3.3.4.2].

11.3.3.5.3 Supportive analyses

Supportive analyses will be similar to those described in Section 11.3.3.4.3 for FSIQ-RMS.

11.3.4 Analysis of the other efficacy variables

The analyses of all exploratory variables will be based on the FAS and described in detail in the SAP. If required, exploratory variables will also be analyzed by subgroups. Each null hypothesis will be tested with a two-sided significance level set to 0.05 in an exploratory manner. All statistical models used will be stratified by baseline EDSS category. For analyses by visit, the observed data will be used as primary analysis and a supportive analysis will use last observation carried forward (LOCF) or other imputation methods where appropriate.

11.3.4.1 Mean number of Gd+ T1, CUAL and new or enlarging T2 lesions by visit

The mean number of Gd+ T1, CUAL and new or enlarging T2 lesions per subject per scan up to Week 48, Week 96, Week 144, EOT and EOS will be analyzed using a negative binomial regression model similar to that described in Section 11.3.3.4.

11.3.4.2 Change in volume of T2 lesions, volume of T1 hypointense lesions and EDSS from baseline to each visit

All variables related to change in lesion volume and change in EDSS at Week 48, Week 96, Week 144, EOT and EOS will be analyzed using an analysis of variance

(ANOVA) with treatment, baseline EDSS category as covariate. Changes to other visits will be summarized descriptively.

11.3.4.3 Absence of Gd+ T1 lesions, absence of new or enlarging T2 lesions, absence of new T1 hypointense lesions and subjects relapse-free

Absence of Gd+ T1 lesions, new T1 hypointense and new or enlarging T2 lesions at Week 48, Week 96, Week 144, EOT and EOS will be analyzed using a logistic regression model with treatment as a factor, including baseline EDSS category as covariate. Subjects that are relapse-free at EOT + 30 days will be analyzed in a similar manner.

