5.1.3 Treatment assignment

A total of 600 eligible subjects will be randomized in a 1:1 ratio to ponesimod 20 mg or placebo, stratified by baseline EDSS score (EDSS ≤ 3.5, EDSS > 3.5).

Each of the study sites will be assigned a unique site number, and every subject will receive a unique screening number (= subject number), which identifies the subject throughout the study. After having confirmed the eligibility of the subject and informed consent has been signed, the investigator/delegate contacts the Interactive Response Technology system (IRT) at Visit 3 to randomize the subject. The IRT assigns a randomization number to the subject, and assigns the treatment kit number which matches the treatment arm assigned by the randomization list to the randomization number.

The randomization list is generated by an independent Contract Research Organization (CRO) and kept strictly confidential.

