7.2.4 Multiple Sclerosis Functional Composite score

The MSFC score consists of three clinical examinations: the Timed 25-Foot Walk, the Paced Auditory Serial Addition Test (PASAT)-3" version, and the 9-Hole Peg Test (9-HPT). The Timed 25-Foot (7.62 meters) Walk is a quantitative measure of lower extremity function. The 9-HPT is a quantitative measure of upper extremity (arm and hand) function. The PASAT is a measure of cognitive function that specifically assesses auditory information processing speed and flexibility, as well as calculation ability.

MSFC will be assessed pre-randomization (see details below) and at Visit 6 (Week 12), Visit 7 (Week 24), Visit 9 (Week 48), and every 24 weeks thereafter until Visit 17 (Week 144), and at Visit 18 (EOT).

During the pre-randomization period, two practice tests and a third test serving as baseline assessment will be performed. Ideally, the three tests should be performed ≥ 5 days apart (i.e., second practice test ≥ 5 days from first practice test and third test serving as baseline ≥ 5 days from second practice test). The first practice test may be done at Visit 1 (Screening), the second practice test may be done at Visit 2 (Baseline) and the third test, serving as baseline, may be performed pre-dose at Visit 3 (Randomization). The MSFC results will be entered by the rater on a specific form which will serve as a source document and the relevant data will be transferred by the site to the eCRF.

MSFC will be administered in combination with the SDMT [see Section 7.2.5] in the following sequence:

1. Timed 25-Foot Walk (7.62 meter)
2. 9-HPT

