11 STATISTICAL METHODS

All statistical analyses will be conducted by Actelion or by designated CROs supervised by Actelion.

The Statistical Analysis Plan (SAP) will be approved prior to database lock for the final analyses. The SAP provides the full details of all analyses, data displays, and algorithms to be used for data derivations.

All data will be listed and endpoints will be summarized by appropriate descriptive statistics (tables or figures), typically including:

- Number of non-missing observations, number of missing observations, mean, standard deviation, median, Q1, Q3, minimum and maximum for continuous endpoints;
- Number of non-missing observations, number of missing observations and frequency with percentage per category (percentages based on the number of non-missing observations) for categorical endpoints;
- Number of subjects at risk, cumulative number of events, cumulative number of censored observations and Kaplan-Meier estimates of the survival function for time-to-event endpoints.

Absolute change from baseline is defined as post-baseline value minus baseline value, i.e., a positive sign indicates an increase as compared to baseline.

A percentage (relative) change from baseline is defined as the absolute change from baseline divided by the baseline value (if the baseline value does not = 0) multiplied by 100.

The baseline value for efficacy is defined as the last non-missing value recorded prior to randomization for each endpoint and each subject individually. The baseline value for safety is defined as the last non-missing value recorded prior to first study drug intake for each endpoint and each subject individually.

The EOS is defined as the date on the end-of-study eCRF page. If this date is missing the last recorded visit on the eCRF is considered as the EOS date.

The EOT date is defined as the date of the last dose of study treatment intake.

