11.3.4.5 NEDA status at EOS

NEDA status at EOS is defined by the absence of confirmed relapses, Gd+ T1 lesions, new or enlarging T2 lesions, 12-week CDA, and an annual brain volume decrease of $\leq 0.4\%$ from baseline to EOS. If at least one of the five criteria is not fulfilled or the subject discontinues treatment prematurely, the subject is not considered to have achieved NEDA. NEDA will be analyzed using a logistic regression model with treatment as a factor and baseline EDSS category included in the model.

11.3.4.6 Change of MSFC Z-score and SDMT score from baseline to EOS by visit

The changes from baseline by visit up to the EOS assessment of both scores are analyzed using an ANOVA, similar to the analyses described in Section [11.3.4.2](#).

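### Change in lesion volume, EDSS, MSFC and SDMT is analysed by ANOVA without the outcome's own baseline value; the test is valid but usually less precise than an ANCOVA on the same data.

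*Protocol*

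**What the plan says.** Section 11.3.4.2 covers "All variables related to change in lesion volume and change in EDSS at Week 48, Week 96, Week 144, EOT and EOS" and prescribes an analysis of variance: "ANOVA) with treatment, baseline EDSS category as covariate". For the MSFC Z-score and SDMT, Section 11.3.4.6 says that the changes by visit up to the EOS "assessment of both scores are analyzed using an ANOVA, similar to the analyses described in Section" 11.3.4.2.

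The response is a simple difference. Section 11 states: "Absolute change from baseline is defined as post-baseline value minus baseline value".

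The only baseline term is the randomisation stratum. The opening of Section 11.3.4 states: "All statistical models used will be stratified by baseline EDSS category". Section 5.1.3 gives the two levels: "stratified by baseline EDSS score (EDSS ≤ 3.5, EDSS > 3.5").

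The baselines themselves are collected. MRI (Section 7.2.3) and EDSS (Section 7.2.1) are done before randomisation. For MSFC, "two practice tests and a third test serving as baseline assessment will be performed" (Section 7.2.4), and Section 7.2.5 says the same for SDMT.

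Section 11.3.4 also says that these analyses are exploratory, that each is tested at a two-sided 0.05, and that the SAP will give the detail.

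**The concern.** A change score uses the baseline only by subtraction, which fixes the slope of follow-up on baseline at 1. When the true slope differs from 1, part of the variation that the baseline could explain stays in the residual and the interval for the treatment effect is wider than it need be. If the arms also happen to differ at baseline by an amount d, the expected difference in change, given that imbalance, is the treatment effect plus (slope − 1) × d. An ANCOVA estimates the slope and removes that term.

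A two-level EDSS category is a weak stand-in for baseline lesion volume, MSFC or SDMT. What is at stake is the width of the intervals on five exploratory outcomes, and a treatment estimate that moves with chance baseline differences.

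**Working it through.** **Inputs.** From the protocol: 600 subjects randomised 1:1, so 300 per arm (Section 11.5.1); change as post-baseline minus baseline (Section 11); the models of Sections 11.3.4.2 and 11.3.4.6; the EDSS cut at 3.5 (Section 5.1.3). The protocol gives no SD, correlation, effect size or power for these outcomes, so it has no figure of its own to reproduce here; its power statements concern the primary endpoint and 12-week CDA. The correlation rho is therefore an assumption, shown over a range.

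**Step 1: general comparison.** Let s0 and s1 be the baseline and follow-up SDs, and b = rho × s1/s0 the slope of follow-up on baseline.

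- Residual variance of the change score: s0² + s1² − 2·rho·s0·s1.
- Residual variance under ANCOVA: s1²(1 − rho²).
- Difference: (s0 − rho·s1)² = s0²(1 − b)².

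The difference is never negative and is zero only when b = 1. In large samples the ANOVA interval is therefore never the narrower one.

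**Step 2: equal SDs, stratum ignored.** With s0 = s1 the ratio of ANCOVA to change-score variance is (1 − rho²)/(2(1 − rho)) = (1 + rho)/2, and the ratio of interval widths is √(2/(1 + rho)). At rho 0.5 the half-widths in SD units are 1.96 × √(1.00 × 2/300) = 0.160 for ANOVA and 1.96 × √(0.75 × 2/300) = 0.139 for ANCOVA, a ratio of 1.155.

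**Step 3: stratum in both models.** The planned model already contains EDSS category, so the fair comparison keeps it on both sides. This was simulated with 600 subjects, 1:1 and equal SDs, 1,500 replicates per setting. For an outcome other than EDSS, the assumptions were a correlation of 0.4 between its baseline and EDSS and 25% of subjects above 3.5. For EDSS itself (treated as continuous), 15%, 25% and 40% above 3.5 were tried.

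Excess width of the ANOVA interval over the ANCOVA interval:

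| rho | Formula, no stratum | Stratum in both, outcome other than EDSS | Stratum in both, EDSS itself |
|---|---|---|---|
| 0.5 | 15.5% | 14.2% | 6.0 to 9.1% |
| 0.7 | 8.5% | 7.7% | 3.2 to 4.9% |
| 0.8 | 5.4% | 4.8% | 2.0 to 3.0% |
| 0.9 | 2.6% | 2.3% | 0.9 to 1.4% |

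**Step 4: what this means for power.** No power is planned for these outcomes, so take a hypothetical effect with 80% power under the ANOVA. Power under ANCOVA is Φ((0.842 + 1.960) × width ratio − 1.960). With the third column's ratios (1.142, 1.077, 1.048, 1.023) it is about 89%, 85%, 84% and 82%.

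**Step 5: unequal SDs.** If lesion volumes grow in proportion to baseline, s1 exceeds s0 and b moves up towards 1. With s1/s0 = 1.25 and rho 0.8, b = 1.25 × 0.8 = 1 and the excess is zero. With s1/s0 = 1.1 it is 4.2% at rho 0.7, 1.6% at 0.8 and 0.0% at 0.9. A simulation with slope exactly 1 gave a width ratio of 0.999: the ANCOVA then costs its one degree of freedom and nothing more.

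**The case against.** The strongest objection is that this is SAP territory: Section 11.3.4 defers the detail of exploratory analyses, Section 11.3.4.6 says only that its ANOVA is similar, and nothing forbids a further covariate. Part of that stands, since the SAP may already add the term. But the protocol names both the method and its terms, so this is a stated choice and not a gap. For CUALs and FSIQ-RMS it announces supportive models with additional baseline covariates; it announces none for these five outcomes.

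The second objection is that nothing here is an error. That stands. A reader might infer that the treatment estimate is biased by regression to the mean. The documents do not support that: allocation is randomised, so chance imbalance averages to zero over repeated allocation and the standard error already allows for it. The loss is precision, and the lack of correction for whatever imbalance does occur.

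Third, the size is assumed. That also stands. It depends on rho, on equal SDs and on the assumed relation to EDSS. A reader might apply the formula's 25%, 15% and 10% variance reductions (rho 0.5, 0.7, 0.8) to all five outcomes. That would be wrong for EDSS, whose stratum is a coarse version of its own baseline, and possibly for both lesion volumes, where the slope may be close to 1.

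**Conclusion.** The point holds as a free gain in precision, not as a flaw in validity. For MSFC and SDMT, and for lesion volumes if their slope is well away from 1, the planned interval is wider by about 14% at rho 0.5, falling to about 2% at rho 0.9. This assumes equal SDs, a correlation of 0.4 with EDSS and a quarter of subjects above 3.5. For EDSS the loss is roughly half that. For lesion volumes it may be nil.

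A reader might also infer that the trial's evidence on disability or lesions is weakened. It is not. Sections 11.2.2 and 11.3.3 put 12-week CDA and CUALs in the confirmatory hierarchy with other models, and the five outcomes here are exploratory under Section 6.1.3. No confirmatory conclusion depends on this choice.

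**What to change.** In Sections 11.3.4.2 and 11.3.4.6, replace the ANOVA by an ANCOVA of change with three terms: treatment, baseline EDSS category, and the continuous baseline value of the same outcome. For change in EDSS, that value is the measured baseline score, kept alongside the category. If the SAP already specifies this, align the protocol wording with it.

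The change costs one degree of freedom per model. It needs no new data or visits and leaves the alpha allocation and the testing hierarchy as they are. It should be fixed before unblinding, so that the choice between adjusted and unadjusted results is not made after seeing them.

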3.5.2 Treatment period

This period consists of a double-blind treatment period, which starts after randomization with the first dose of study treatment during Visit 3 (Day 1 of study).

The double-blind treatment period has a variable duration from a minimum of 60 weeks (for the last subject randomized) to a maximum of 156 weeks (3 years) for the first subjects randomized in the trial. Average duration is expected to be approximately 2 years. It includes a randomization visit, visits at 2, 4 and 12 weeks after randomization, and 12-weekly visits thereafter until 60 weeks after the randomization of the last subject or 156 weeks of treatment (whichever occurs first).

For an individual subject, this period starts on the day of the first study treatment intake and continues until the premature discontinuation of study treatment, Week 156, or until 60 weeks after the randomization of the last subject (whichever occurs first).

EOT visit: The EOT visit at an individual level should preferably take place 1 day after the last dose of study treatment, but no later than 7 days after the last dose of study treatment.

3.5.2.1 *Modification of treatment*

If a subject meets one of the following conditions:

- The subject has experienced a confirmed relapse while on study treatment;
- The subject has experienced an event of 24-week CDA while on study treatment;

Then, the principal investigator / treating neurologist should consider and propose the following options to this subject:

- Subject remains on study treatment. In this case, the subject will be asked to re-consent to continue receiving study treatment [see Section 13.3].
- Subject prematurely discontinues study treatment and DMF background therapy, and begins treatment with an approved MS therapy at the discretion of the treating neurologist in accordance with local practices. In this case, the subject will enter the post-treatment observation period (PTOP) of the study [see Section 3.5.3.2].

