3.5.3.2 Post-treatment observation period

Subjects who prematurely discontinue study drug and complete the 30-day safety follow-up including the FU visit, will enter the PTOP which lasts until 60 weeks after randomization of the last subject or until Week 156, whichever is first (i.e., planned EOT visit) irrespective of treatment completion. It consists of an abbreviated schedule of assessments at the time of the originally scheduled 12-weekly visits. The aim is to

follow-up with the subjects after discontinuation of study treatment and to collect long-term data while the subject possibly receives other approved MS therapies.

While participating in the PTOP, subjects may not be enrolled in another clinical trial. They may, however, withdraw their consent to participate to this study at any time [see Section 9.2].

3.5.3.3 *End-of-Study*

[figure not shown]
The study level EOS will occur after all subjects have completed the safety FU period or the last visit of the PTOP.

For an individual subject, EOS is reached when treatment, post-treatment safety FU, and if applicable, the PTOPs have been completed:

- For subjects who complete the treatment period, and for subjects who prematurely discontinue study treatment and do not enter the PTOP, the EOS visit corresponds to the 30-day FU visit (FU).
- For subjects who prematurely discontinue study treatment and enter the PTOP period, the EOS visit corresponds to the last visit of the PTOP.

The overall study design is shown in [Figure 1](#).

Figure 1 AC-058B302 study design

D = day; DMF = dimethyl fumarate; EOS = End-of-Study; EOT = End-of-Treatment; FU = follow-up; V = visit; W = week; *Lymphocyte tests every 4 weeks (\pm 3 days) until Week 24; ** Subjects participating in the lymphocyte subset sub-study will have an additional FU visit approximately 7 days after the last dose of study drug (FU7d).

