6.1.3 Other efficacy endpoints

MRI-based exploratory endpoints:

- Percent change in brain volume (PCBV) from baseline to Weeks 48, 96, 144, EOT, and EOS;
- Mean number of CUALs per subject per scan from baseline up to Weeks 48, 96, 144, EOT, and EOS;
- Mean number of Gd+T1 lesions per subject per scan from baseline up to Weeks 48, 96, 144, EOT, and EOS;
- Mean number of new or enlarging T2 lesions per subject per scan from baseline to Weeks 48, 96, 144, EOT and EOS;
- Change in the volume of MRI lesions (T2 lesions, T1 hypointense lesions) from baseline to Weeks 48, 96, 144, EOT, and EOS;
- Absence of MRI lesions (Gd+ T1 lesions, new or enlarging T2 lesions, new T1 hypointense lesions) from baseline to Weeks 48, 96, 144, EOT, and EOS.

Clinical exploratory endpoints (disease activity, relapses, disability progression):

- Absence of confirmed relapses from baseline up to EOS;
- Time to first 24-week CDA from baseline up to EOS;

Definition: A 24-week CDA is:

- an increase of at least 1.5 in EDSS for subjects with a baseline EDSS score of 0, or
- an increase of at least 1.0 in EDSS for subjects with a baseline EDSS score of 1.0 to 5.0, or
- an increase of at least 0.5 in EDSS for subjects with a baseline EDSS score ≥ 5.5 ,

which is to be confirmed after 24 weeks.

Baseline EDSS is defined as the last EDSS score recorded during pre-randomization. The initial EDSS increase, meeting the above criteria, is defined as the onset of disability accumulation. All EDSS measurements (with or without relapse, at a scheduled or unscheduled visit) will be used to determine the onset of disability accumulation.

However, for the purpose of confirmation, only EDSS measured more than 30 days after the onset of a confirmed relapse will be used. This is to avoid a confirmation of disability accumulation caused by a relapse. In order to confirm that the EDSS increase is persistent, all EDSS measurements between the onset and the 24-week EDSS confirmation (minus visit time-window) need to show an increase in EDSS, meeting the criteria for accumulation of disability as defined above.

- Change in EDSS from baseline by visit up to EOS;
- No evidence of disease activity (NEDA) status at EOS (defined by the absence of confirmed relapse, Gd+ T1 lesions, new or enlarging T2 lesions, 12-week CDA, as well as absence of annual brain volume decrease $\geq 0.4\%$ from baseline to EOS and completing treatment as planned).

Other clinical exploratory endpoints:

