9.2 Premature withdrawal from study

Subjects may voluntarily withdraw from the study for any reason at any time. Subjects are considered withdrawn if they state an intention to withdraw further participation in all components of the study (i.e., withdrawal of consent), die or are lost to FU for any other reason. If a subject withdraws consent, no further data will be collected in the eCRF from the date of withdrawal onward. The investigator may withdraw a subject from the study (without regard to the subject's consent) if, on balance, they believe that continued participation in the study would be contrary to the best interests of the subject. Withdrawal from the study may also result from a decision by Actelion for any reason, including premature termination or suspension of the study [see Section 9.3].

A subject who prematurely discontinues study drug is not considered as withdrawn from the study and will enter the PTOP period consisting of an abbreviated schedule of assessments, at the time of the originally scheduled 12-weekly visits.

Subjects are considered as lost to FU if all reasonable attempts by the investigator to communicate with the individual fail. The site must take preventive measures to avoid a subject being lost to FU (e.g., document different ways of contact such as telephone

number, home address, e-mail address, person to be contacted in case the subject cannot be reached). If the subject cannot be reached, the site must make a reasonable effort to contact the subject, document all attempts and enter the loss of FU information into the eCRF. The following methods must be used: at least three telephone calls must be placed to the last available telephone number, and one registered letter must be sent by post to the last available home address. Additional methods may be acceptable if they are compliant with local rules/regulations (e.g., site staff visit to the subject's home), respecting the subject's right to privacy. If the subject is still unreachable after all contact attempts listed above, she/he will be considered to be lost to FU.

If premature withdrawal occurs for any reason, the reason for premature withdrawal from the study along with who made the decision (subject, investigator or Actelion) must be recorded in the eCRF.

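### Relapse-free status is defined up to EOS in section 6.1.3 but analysed only at EOT + 30 days in section 11.3.4.3, so relapses recorded after early stopping are ignored

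*Protocol*

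**What the plan says.** The synopsis and section 6.1.3 list the endpoint as "Absence of confirmed relapses from baseline up to EOS".

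Section 11.3.4.3 covers the yes/no endpoints. Absence of lesions is assessed at Weeks 48, 96 and 144, at EOT and at EOS, and "will be analyzed using a logistic regression model with treatment as a factor, including baseline EDSS category as covariate". The sentence on relapses follows: "Subjects that are relapse-free at EOT + 30 days will be analyzed in a similar manner". EOS is not named for relapse-free status, and the model has no term for length of observation. Section 11.3.4 sets the status of these tests: "Each null hypothesis will be tested with a two-sided significance level set to 0.05 in an exploratory manner".

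Three other provisions decide how far the two time points differ:

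- Section 11: "The EOT date is defined as the date of the last dose of study treatment intake".
- Section 9.2: "A subject who prematurely discontinues study drug is not considered as withdrawn from the study and will enter the PTOP period". Section 7.2.2 and Table 3 keep relapse detection and EDSS assessment going in that period.
- Section 3.5.3.3: "For subjects who complete the treatment period, and for subjects who prematurely discontinue study treatment and do not enter the PTOP, the EOS visit" is the 30-day follow-up visit. For completers, EOT + 30 days and EOS therefore nearly coincide. For subjects who stop early and enter the PTOP they do not.

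**The concern.** The protocol fixes two different windows for one endpoint, so leaving detail to the SAP does not settle which applies.

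The analysed window ends at an event that happens after randomisation and can depend on treatment. A subject who stops on Day 1 is observed for about a month; a completer is observed for 60 to 156 weeks plus the follow-up. The shorter the window, the more likely a subject is to be free of relapse, and the model does not account for this. Relapses that the trial goes on to collect in the PTOP are left out.

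At stake is a relapse-free percentage and odds ratio that are easy to quote. They could differ from the trial's own EOS results for reasons unrelated to drug effect.

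**Working it through.** **1. How the protocol treats the two windows elsewhere**

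| Outcome | Main window | EOT + 30 days |
|---|---|---|
| ARR (11.3.2.2.1, 11.3.2.4) | EOS | supportive |
| 12-week CDA (11.3.3.1) | EOS | supportive |
| Time to first confirmed relapse (11.3.3.2) | EOS | supportive |
| NEDA (11.3.4.5) | EOS, early stopping counts as failure | not used |
| Relapse-free (11.3.4.3) | defined to EOS, no EOS analysis named | the only analysis |

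**2. Which subjects are classified differently**

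- Relapse on drug, then stop: not relapse-free under either window.
- Stop before any relapse, relapse within 30 days of the last dose: not relapse-free under either window.
- Stop before any relapse, relapse later in the PTOP: relapse-free at EOT + 30 days, not relapse-free at EOS.

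Only the third group matters.

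**3. The plan's own figure**

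The protocol gives no figure for this endpoint, so the relapse model was checked against the primary power in section 11.5.1 (300 per arm, ARR 0.50 and 0.325, k = 1.3, mean follow-up 1.9 years). Information per arm is n·λt/(1 + kλt).

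- Placebo: 300 × 0.95/(1 + 1.3 × 0.95) = 127.5
- Ponesimod: 300 × 0.6175/(1 + 1.3 × 0.6175) = 102.8
- SE of log rate ratio: √(1/127.5 + 1/102.8) = 0.1326
- Power: Φ(0.4308/0.1326 − 1.96) = Φ(1.29) = 90.1%, against about 90% stated

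**4. Relapse-free proportion**

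Under the same model, the probability of no relapse over a window W is (1 + kλW)^(−1/k), averaged over W.

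- From the protocol: λ = 0.50, k = 1.3, 300 per arm, planned treatment T of 60 to 156 weeks.
- Assumed: T uniform over that range; stopping time D exponential with hazard −ln(1 − d), where d is the annual stopping proportion, independent of relapse; no withdrawal from the study itself.
- Window A: EOS at T + 30 days, and EOT + 30 days at min(T, D) + 30 days. This follows section 3.5.3.3.
- Window B, as a check: EOS at T, and EOT + 30 days at min(T, D + 30 days).

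With no drug effect (ARR 0.50 in both arms):

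| Window | Assumed d, placebo / ponesimod | Relapse-free at EOS, both arms | At EOT + 30 days, placebo / ponesimod | OR | Rejection at nominal 5% |
|---|---|---|---|---|---|
| A | 10% / 10% | 51.8% | 55.3% / 55.3% | 1.00 | 5% |
| A | 10% / 20% | 51.8% | 55.3% / 58.7% | 1.15 | 13% |
| B | 10% / 20% | 52.7% | 56.0% / 59.3% | 1.14 | 13% |
| B | 10% / 30% | 52.7% | 56.1% / 62.5% | 1.30 | 36% |

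Arithmetic for the second row:

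- OR = (0.587/0.413)/(0.553/0.447) = 1.421/1.237 = 1.15
- SE of the difference = √(0.553 × 0.447/300 + 0.587 × 0.413/300) = 0.0404
- z = 0.034/0.0404 = 0.84
- Rejection = Φ(0.84 − 1.96) + Φ(−0.84 − 1.96) ≈ 13%

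Subjects with a later relapse who are counted as relapse-free: 55.3 − 51.8 = 3.5 points in placebo (about 10 of 300) and 58.7 − 51.8 = 6.9 points in ponesimod (about 21 of 300). If the two rates are swapped between arms, the OR is 1/1.15 = 0.87.

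**5. Stopping caused by relapse**

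No drug effect, window B, 10% per year other stopping in both arms. Half of placebo relapsers stop after their first relapse and no ponesimod relapsers do. Discontinuation is 38% versus 19%, yet relapse-free status at EOT + 30 days is 56.0% versus 56.1%.

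**6. Planned effect (0.50 versus 0.325), window B**

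The OR is 1.48 at EOS. At EOT + 30 days it is 1.47 with 10% stopping in both arms and 1.67 with 10% versus 20%.

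**The case against.** **Relapse-free experience to EOS is already analysed.** Time to first confirmed relapse up to EOS is a ranked secondary endpoint. Section 11.3.3.2.2 plans a stratified log-rank test, a hazard ratio and Kaplan-Meier estimates at 12-week intervals, which include Weeks 48 and 96. This stands. A reader might infer that the endpoint would go unanalysed; what is missing is only the binary analysis at EOS.

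**More discontinuation does not by itself flatter an arm.** A reader might infer that whichever arm stops more will look better. Step 5 shows otherwise: section 3.5.2.1 makes a confirmed relapse a trigger for offering a switch, and that relapse is already counted. Only stopping before a first relapse matters.

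**The imbalance is assumed.** The protocol states no discontinuation rate for this trial. Section 1.3.2.4 says no Phase 2 patient on 20 mg stopped for a respiratory event, and section 3.3 describes discontinuations at 20 mg as similar to 10 mg. Neither compares overall stopping with placebo. Several mandatory stopping criteria are unrelated to relapse (failed cardiac discharge in 5.1.10, lymphocyte thresholds in 5.1.12.2, macular edema in 5.1.12.7), so an imbalance is plausible but not established.

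**The endpoint is exploratory.** It lies outside the testing hierarchy, so a raised nominal error rate changes no confirmatory conclusion. This stands and limits the weight of the point.

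None of this removes the mismatch between sections 6.1.3 and 11.3.4.3.

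**Conclusion.** The inconsistency is real: the endpoint is defined to EOS, and its only specified analysis stops at EOT + 30 days and disregards relapses recorded later. The bias is conditional. It needs a difference between arms in stopping before a first confirmed relapse, and it favours the arm with more such stopping. With no drug effect and an assumed 10% versus 20% per year, the OR is about 1.15 and rejection about 13%; with equal rates the OR is 1.00. These figures rest on the protocol's ARR and dispersion, uniform follow-up of 60 to 156 weeks, stopping independent of relapse and the assumed rates. Size and direction in this trial are not known.

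The primary ARR and time to first confirmed relapse are untouched. Two wider readings are not supported:

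- That lesion-free status has the same fault. Sections 6.1.3 and 11.3.4.3 agree on its EOT and EOS windows.
- That a complementary log-log model with log follow-up as offset is needed. Such an offset implies a probability of exp(−λt), which does not match the overdispersed model with k = 1.3. Simulated type I error of the unadjusted comparison at EOS was 4.3% to 4.9%.

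**What to change.** In section 11.3.4.3, analyse relapse-free status up to EOS, as section 6.1.3 and the synopsis define it. The same logistic model is acceptable there, because planned follow-up does not depend on stopping drug. Read it alongside the Kaplan-Meier proportions already planned in section 11.3.3.2.2, which also handle subjects who withdraw from the study before its end. Keep EOT + 30 days as a supportive analysis, as the protocol does for the ARR, and carry the same wording into the SAP.

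The cost is one sentence in the protocol and the matching SAP text. The relapse data up to EOS are already collected, so no new assessments are needed.
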